### **Objective**

The goal of this study is to test the non-inferiority of Brief Behavioral Treatment for Insomnia (BBTI) versus the current gold standard treatment for insomnia, Cognitive Behavioral Therapy for Insomnia (CBTI).

### Design

This study is a prospective non-inferiority randomized clinical trial.

## Hypotheses

- 1. Both BBTI and CBTI will significantly reduce insomnia symptoms, per the Insomnia Severity Index (ISI), from pre- to post-treatment.
- 2. BBTI will be non-inferior to CBTI based on ISI change score from pre- to post-treatment.

## Methodology

## **Participants**

Veterans with chronic insomnia were recruited. Eligible Veterans were ≥18 years, met Diagnostic and Statistical Manual of Mental Disorders, 5th edition (DSM-5) criteria for insomnia disorder (First, Williams, Karg, & Spitzer, 2015), and had an ISI ≥15 (Bastien, Vallieres, & Morin, 2001).

Veterans were excluded if they had: current or past bipolar, psychotic, or seizure disorder; alcohol use disorder or substance use disorder in the past six months; other current, severe, and unstable and/or untreated psychiatric and/or medical disorders; been hospitalized, for any reason, in the past month; untreated sleep apnea and/or other untreated non-insomnia sleep disorders; moderate to severe cognitive impairment; homeless or unstable housing; shift workers; or if female, were pregnant.

This study was designed to enroll Veterans who would typically be eligible to engage in CBTI at a VAMC and was similar to the guidelines as part of the VA CBTI training program (Manber et al., 2014).

#### **Procedures**

All study procedures took place at VA Pittsburgh Healthcare System (VAPHS); recruitment, treatment, post-treatment, and 3-month follow-up took place May 2016 through June 2019, with 12-month follow-up through March 2020. Participants were recruited with advertisements, by invitation from practicing insomnia providers, and with postings on Craigslist.com.

Eligible Veterans, after a brief phone or in-person screen, were invited for an in-person appointment to sign informed consent and complete diagnostic interviews and self-report measures. Assessment of insomnia and other sleep disorders was conducted using the South Texas Research Organizational Network Guiding Studies on Trauma and Resilience (STRONG STAR) Clinical Interview for DSM-5 Sleep-Wake Disorders (Taylor et al., 2018). Risk for obstructive sleep apnea (OSA) was assessed using the STOP-BANG questionnaire (Chung et al., 2012); Veterans scoring ≥5 and/or had untreated OSA were excluded and referred to the Sleep Medicine Clinic. Cognitive impairment was assessed using the St. Louis University Mental Status Examination (SLUMS; Tariq, Tumosa, Chibnall, Perry 3rd, & Morley, 2006); Veterans with scores ≤20, indicative of serious cognitive impairment, were excluded. Finally,

psychiatric disorders were assessed using the Structured Clinical Interview for DSM-5, Research Version (SCID-5-RV; First et al., 2015).

## Randomization and Sample Size

Veterans were randomized to BBTI or CBTI in a 1:1 manner, in random block sizes of 2, 4, or 6, stratified by age (18-64 or ≥65) and use of a prescription sedative-hypnotic medication (yes or no). Sequentially numbered envelopes were used to assign participants based on their strata with concealment until randomization. Participants were enrolled by the Principal Investigator with the randomization strategy developed by the study statistician using Stata v14 and group assignment by the study coordinator.

Sample size was calculated based on non-inferiority methods (Julious, 2004) and was further informed by the calculation of a non-inferiority margin (NIM), the pre-specified difference between treatments that demonstrates BBTI is not unacceptably worse than CBTI (Schumi & Wittes, 2011). The Reliable Change Index (RCI; Jacobson & Truax, 1991; Sloan, Marx, Lee, & Resick, 2018) measures change at post-treatment not due to error, and for this study was calculated for the "control" condition (CBTI) using VA rollout data (Trockel et al., 2014). The RCI equation uses a measure of reliability (internal consistency or test-retest reliability) for the outcome measure, in this case the ISI. The RCI for CBTI was calculated using both reliability metrics to create a range of NIMs. Using Cronbach's alpha ( $\alpha$ =0.905; Morin, Belleville, Belanger, & Ivers, 2011) the RCI was 5.21 and using the test-retest reliability (r=0.78; Savard, Savard, Simard, & Ivers, 2005) the RCI was 3.43. We chose the NIM of 3.43. Accounting for 25% attrition, based on prior CBTI and BBTI studies (Buysse et al., 2011; Germain et al., 2014; Trockel et al., 2014) the target randomization goal was 56 participants (n=28/group) with 42 (n=21/group) completing post-treatment assessment to achieve 80% power.

#### Clinician Training

Study clinicians attended a half-day training by the Principal Investigator and study Co-Investigator; CBTI and BBTI trainings were separate and study clinicians only received one training. CBTI (Manber et al., 2014) was delivered in 5 in-person sessions, weekly or bi-weekly, with a goal of completing treatment in 8 weeks. The components included psychoeducation, sleep health education, stimulus control, sleep restriction, cognitive restructuring of maladaptive beliefs, and relaxation strategies as needed. Sleep diaries were completed daily throughout treatment, beginning with the baseline assessment. Increasing prescribed time in bed (TIB) occurred if sleep efficiency (SE) was ≥85%, in which case TIB was increased 15 minutes (if wanted by participant). CBTI was delivered by two licensed psychologists, one who delivered care in the Mental Health Clinic and another in Primary Care.

## Interventions

BBTI (Troxel et al., 2012) includes one to two in-person sessions (session 1 and 3; week 3 is optional by phone) and two phone sessions (sessions 2 and 4) and will occur within 5 weeks.

Session 1 (45 minutes, in person). Background information is provided about healthy sleep practices
and the mechanisms of sleep regulation as well as the principles of stimulus control, sleep
restriction, and sleep hygiene. Baseline sleep diaries will determine initial sleep parameters (e.g.,
bedtime, wake time, sleep onset latency, sleep efficiency). Lastly, the four "rules" are introduced
and discussed.

- Reduce your time in bed. Sleep diaries will determine the prescribed bedtime, with the goal
  to match time in bed to time asleep (plus an additional 30 minutes to account for a normal
  amount of time spent awake at night). Reducing time in bed helps to increase the
  homeostatic sleep drive.
- Wake up at the same time every day. A consistent wake time is a) the most important cue
  for setting the biological clock, b) regulates exposure to morning light (another cue for the
  biological clock), and c) helps to increase the homeostatic sleep drive.
- Do not go to bed unless sleepy. By waiting until the sleep drive is at its peak, the likelihood of falling asleep is increased. The key is helping the Veteran understand the difference between sleepiness and fatigue/tiredness. The bedtime is restricted by the prescribed bedtime set by the sleep diaries as well as a state of sleepiness. Bedtime is not determined by when the Veteran "should" go to sleep.
- Do not stay in bed unless asleep. By saving the bed for sleep and sexual activity only, the association between the bed and sleep is strengthened. Staying in bed while awake perpetuates the cycle of wakefulness → frustration → arousal → wakefulness. This cycle is broken by staying out of bed if awake. The recommendation is to get out of bed if awake for longer than 30 minutes (self-estimation).
- Session 2 (<20 minutes, phone call). This is a check-in regarding changes in sleep/wake behaviors
  implemented in session 1. The clinician and Veteran will discuss the sleep diary from the past week,
  discuss adherence to the "rules," and problem-solve any adherence issues.

- Session 3 (<30 minutes, in person or by phone). The Veteran and clinician will review the past two weeks of sleep diaries and adjust the sleep schedule as needed. If SOL and WASO are <30 minutes for most nights during the previous two weeks, the Veteran can extend their sleep schedule by 15 minutes, either advancing the bedtime or delaying the wake time. If SOL/WASO is >30 minutes for most nights, sleep schedule is restricted by 15 minutes. Adherence to treatment recommendations is reinforced.
- Session 4 (<20 minutes, phone call). The final session, a phone call, addresses treatment difficulties, reviews the progress made, and covers relapse-prevention techniques. The concepts of stimulus control and sleep restriction are emphasized, as is the process of titrating sleep using the 30/30 rule.

CBTI (Manber et al., 2014) consists of five sessions, about 45-minutes each, and will occur within an 8-week period.

- Session 1. Basic sleep education, including a review of the predisposing, precipitating, and perpetuating factors of insomnia (3P model of insomnia). The homeostatic sleep drive and circadian drive are explained. Next, stimulus control, sleep restriction, and sleep hygiene are reviewed; these concepts provide the basic structure to improve insomnia.
  - Wake-up and get out of bed at the same time every day. A consistent wake time is a) the
    most important cue for setting the biological clock, b) regulates exposure to morning light,
    and c) helps to increase the homeostatic sleep drive for subsequent nights.
  - Go to bed when you are sleepy, but not before a prescribed bedtime. By waiting until the sleep drive is at its peak, the likelihood of falling asleep is increased.

- Get up when you can't sleep. Staying in bed while awake perpetuates the cycle of wakefulness à frustration à arousal à wakefulness. When unable to sleep, it is recommended to get out of bed and go to another room until sleepiness returns.
- Use the bed only for sleeping. By saving the bed for sleep and sexual activity only, the
  association between the bed and sleep is strengthened. Avoid TV, reading, work, etc., while
  in bed.
- Avoid daytime napping, particularly in the late afternoon or early evening. Sleep during the
  day can reduce the homeostatic sleep drive and make it more difficult to fall asleep at the
  desired bedtime.
- Create a buffer zone. This is a quiet time prior to bedtime that can help to reduce stress. It
  provides a transition between the goal-oriented activities of the day and the quiet more
  peaceful time of sleep.
- Don't worry, plan, etc., in bed. Avoid any stressful, worrisome, or stimulating activities in bed. Preoccupation with worries, problems, or planning can increase arousal and interfere with sleep.
- Other helpful practices/sleep hygiene. Recommendations include: turn the clock around, limit caffeine in the afternoon, limit alcohol within 3 hours of bedtime, exercise regularly but not close to bedtime, keep bedroom quiet, dark, and cool, avoid heavy meals close to bedtime but don't go to bed hungry.
- Session 2. Sleep diaries are reviewed, and prescribed bedtime is titrated based on sleep efficiency. If sleep efficiency <80%, time in bed is reduced by 15 minutes. If sleep efficiency ≥85%, time in bed is increased by 15 minutes. Problem-solving and motivational enhancement is used for any adherence issues. Additional handouts include information on what to do when awake (night and morning), enjoying your morning, and reasons for feeling tired.

- Session 3-4. Sessions 3 and 4 are focused on continued titration of the sleep schedule, monitoring adherence to treatment guidelines (1-8 above), and identifying and challenging dysfunctional beliefs about sleep (DBAS questionnaire), such as: "I need 8 hours of sleep per night" or "Insomnia has serious health consequences." Identifying and challenging automatic thoughts about sleep is can also be helpful. Lastly, relaxation (active or passive) may be introduced and practiced.
- Session 5. Continue titrating time in bed, cognitive restructuring, and relaxation as needed. If improvements have been appropriate, session 5 may focus on relapse prevention, summarizing gains, and discussing what was, or was not, helpful. Elements of relapse prevention include: keep a consistent wake time; go to bed only when sleepy, but not before the regular bedtime; and get out of bed if unable to sleep.

## Measures

The primary outcome measure was the ISI (Bastien et al., 2001), administered at baseline, in-person treatment sessions, one-week post-treatment, and the 3-month and 12-month follow-up assessments.

The Consensus Sleep Diary (Carney et al., 2012) was used to collect data on sleep behaviors, including bedtimes, rise times, sleep onset latency (SOL), nighttime awakenings (NWAK), wake after sleep onset (WASO), time in bed (TIB), total sleep time (TST), total wake time (TWT), sleep efficiency (SE), and sleep

quality (SQ). Diaries were administered for two weeks of baseline, during treatment, two weeks after the post-treatment assessment, and the 3-month and 12-month assessments.

Additional sleep measures administered at baseline, post-treatment, 3-month and 12-month assessments included the Pittsburgh Sleep Quality Index (PSQI; Buysse, Reynolds, Monk, Berman, & Kupfer, 1989) as a measure of sleep quality, the Dysfunctional Beliefs and Attitudes about Sleep scale (DBAS; Morin, Vallieres, & Ivers, 2007) to assess sleep-disruptive cognitions, and the Epworth Sleepiness Scale (ESS; Johns, 1991) to assess daytime sleepiness.

Self-report measures of psychiatric symptoms included the Patient Health Questionnaire 9 (PHQ9; Kroenke, Spitzer, & Williams, 2001) to assess depression, the Generalized Anxiety Disorder 7 (GAD7; Spitzer, Kroenke, Williams, & Lowe, 2006) to assess anxiety, and the PTSD Checklist for DSM-5 (PCL5; Blevins, Weathers, Davis, Witte, & Domino, 2015) to assess symptoms of PTSD. Additional measures included the Patient Reported Outcome Measurement Information System (PROMIS) Fatigue Scale (Reeve et al., 2007) to assess fatigue and its impact on functioning and quality of life, a brief pain scale measuring pain intensity (P), interference with enjoyment of life (E), and interference with general activity (G [PEG]; Krebs et al., 2009), the PROMIS Global Health Scale (Hays, Bjorner, Revicki, Spritzer, & Cella, 2009) to measure the impact of physical health (QOL-PH) and mental health (QOL-MH) on quality of life, the Work and Social Adjustment Scale (WSAS; Mundt, Marks, Shear, & Greist, 2002) to measure psychosocial functioning impairment due to insomnia, and the Patient Global Impression of Change (PGIC; Hurst & Bolton, 2004). Psychiatric symptom and psychosocial measures were administered at baseline, post-treatment, and 3-month and 12-month assessments.

## Summary of self-report measures

Measure	Items	Score Range	Desired Direction
ISI	7	0-28	→
PSQI	18	0-21	$\downarrow$
ESS	8	0-24	$\downarrow$
DBAS ∥	16	0-10	$\downarrow$
PHQ9 ‡	8	0-24	$\downarrow$
GAD7	7	0-21	$\downarrow$
PCL5 ‡	19	0-76	$\downarrow$
Fatigue †	6	33.4-76.8	$\downarrow$
PEG	3	0-30	$\downarrow$
QOL-PH †	4	16.2-67.7	$\uparrow$
QOL-MH †	4	21.2-67.6	$\uparrow$
WSAS	5	0-40	$\downarrow$
PGIC	7	1-7	$\uparrow$

Notes: || average score; | sleep item removed; | T scores

ISI, Insomnia Severity Index; PSQI, Pittsburgh Sleep Quality Index; ESS, Epworth Sleepiness Scale; DBAS, Dysfunctional Beliefs and Attitudes about Sleep; PHQ9, Patient Health Questionnaire; GAD7, Generalized Anxiety Disorder; PCL5, Posttraumatic Stress Disorder Checklist; PEG, pain intensity, interference with enjoyment of life, and interference with general activity; QOL-PH, Quality of Life – Physical Health; QOL-MH, Quality of Life – Mental Health; WSAS, Work and Social Adjustment Scale; PGIC, Patient Global Impression of Change.

### **Statistical Analysis Plan**

Analyses were conducted with STATA v14. Baseline differences between CBTI and BBTI were analyzed using chi-square tests and t-tests.

To test treatment effectiveness, an intent-to-treat (ITT, n=63) and per-protocol (PP, n=24) approach were used. Consistent with ITT, all individuals randomized, regardless of their completion status, were encouraged to complete the post-treatment and follow-up assessments.

PP analyses were conducted on Veterans in each group that met strict criteria—attending all treatment sessions within the time frame defined *a priori* (BBTI: n=12, 4 sessions in 5 weeks; CBTI: n=12, 5 sessions in 8 weeks) and completing the one-week post-treatment assessment.

Linear mixed models (LMM) were used to test the main effects of treatment (CBTI vs. BBTI), time (baseline vs. post-treatment), and the interaction of treatment X time. Effect sizes were computed using Glass's  $\Delta$  ( $|M_{pre} - M_{post}|/SD_{pre}$ ; Morris, 2008).

Treatment response was an ISI reduction at post-treatment of  $\geq 8$  points (indicating a moderate response), and remission was a treatment response plus an ISI score  $\leq 7$  at post-treatment (indicating no clinically significant insomnia symptoms; Morin et al., 2011).

To establish BBTI as non-inferior to CBTI, the upper bound of the 95% confidence interval of the mean  $\Delta$ ISI from pre- to post-treatment ( $\Delta$ ISICBTI –  $\Delta$ ISIBBTI) cannot exceed the NIM of 3.43. If the upper bound of the confidence interval exceeds the NIM, non-inferiority cannot be declared (inconclusive). If the lower bound of the confidence interval exceeds the NIM, BBTI will be declared inferior to CBTI. However, should the upper bound of the confidence interval not exceed zero, BBTI will be declared superior to CBTI (Aberegg, Hersh, & Samore, 2018).

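### Must the SAP say whether ITT or per-protocol decides non-inferiority, and make ITT the sole judge?

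*Combined protocol and SAP*

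**What the plan says.** Hypothesis 2, under Hypotheses, states that "BBTI will be non-inferior to CBTI based on ISI change score from pre- to post-treatment" and names no analysis set. Under Statistical Analysis Plan, "an intent-to-treat (ITT, n=63) and per-protocol (PP, n=24) approach were used" to test effectiveness. The decision rule later in that section begins "To establish BBTI as non-inferior to CBTI, the upper bound of the 95% confidence interval of the mean" change difference (CBTI minus BBTI), which may not go above 3.43; again no set is named. A bound above the margin has a stated reading: "If the upper bound of the confidence interval exceeds the NIM, non-inferiority cannot be declared (inconclusive". Inferiority is declared only if the lower bound lies above the margin.

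Three other statements bear on the choice of set.
- Randomization and Sample Size sets the target "with 42 (n=21/group) completing post-treatment assessment to achieve 80% power", with no condition on attendance or timing.
- The Statistical Analysis Plan says that "all individuals randomized, regardless of their completion status, were encouraged to complete the post-treatment and follow-up assessments".
- It defines the per-protocol group by attendance within a time window: "BBTI: n=12, 4 sessions in 5 weeks; CBTI: n=12, 5 sessions in 8 weeks", plus the one-week post-treatment assessment.

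**The concern.** Two analysis sets and one rule allow three readings: ITT decides, per-protocol decides, or both must pass. The sets differ greatly in size, since per-protocol keeps 24 of 63 and drops 39 (62%). The same point estimate can therefore clear the margin in one set and miss it in the other through interval width alone. If so, a reader could not tell from the plan which result is the trial's conclusion. An author could lean on whichever set is favourable, and the design figures would shift with the reading: power falls if both sets must pass, and type I error rises if either may. The natural remedy would be to name ITT as the deciding set and give per-protocol neither a veto nor a rescue.

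**Working it through.** **Inputs.** From the documents: margin 3.43; 95% interval, so one-sided 0.025 for the rule; 21 per arm assessed for 80% power; 25% attrition; ITT 63; per-protocol 12 per arm. Assumed, because not stated: the SD of ISI change, a true difference of zero, equal SD in both sets, and an even split of the 63 (31.5 per arm).

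**The plan's own figure.** The attrition step reproduces: 21/0.75 = 28 and 42/0.75 = 56. The 21 per arm cannot be reproduced without an SD. Solving backwards:
- SD = 3.43 × √(21/2) / (1.960 + 0.842) = 3.97 at one-sided 0.025.
- At one-sided 0.05 the same step gives 4.47. At that SD the 95% interval rule has about 70% power at 21 per arm.

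**Largest estimate that still passes.** Formula: 3.43 − c × SD × √(2/n), with SD 3.97 and c the normal or t critical value.

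| Per arm | Half-width (z, t) | Largest passing estimate (z, t) | Upper bound if the estimate is 0.5 (z, t) |
|---|---|---|---|
| 12 (per-protocol) | 3.17, 3.36 | 0.26, 0.07 | 3.67, 3.86 |
| 21 (42 assessed) | 2.40, 2.47 | 1.03, 0.96 | 2.90, 2.97 |
| 31.5 (all 63) | 1.96, 2.00 | 1.47, 1.43 | 2.46, 2.50 |

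An estimate of 0.5 thus passes in ITT and is inconclusive in per-protocol. The example depends on the SD: at SD 3.5 (z), per-protocol passes up to 0.63, so both sets pass.

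**How often the sets disagree.** Treat per-protocol as a random subset of ITT, with correlation √(12/n) between the two estimates, SD 3.97 and no true difference. The middle row applies 25% attrition to 63: 63 × 0.75 = 47.25, or 23.6 per arm.

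| ITT per arm | ITT passes | PP passes | Both pass | ITT only | PP only | Any split |
|---|---|---|---|---|---|---|
| 21 | 80% | 56% | 54% | 26% | 2.2% | 28% |
| 23.6 | 84% | 56% | 55% | 30% | 1.7% | 32% |
| 31.5 | 93% | 56% | 56% | 37% | 0.7% | 38% |

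Over SD 3.5 to 8 with no true difference, the split probability runs from 19% to 43%. The 43% needs post-treatment ISI on all 63; with attrition applied, the top is 33%. Nearly all splits at SD 3.97 are an ITT pass beside an inconclusive per-protocol result.

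**What making ITT sole judge would cost.** Suppose a true difference equal to the margin is diluted by 25% through non-adherence, to 3.43 × 0.75 = 2.57. The chance that ITT declares non-inferiority is Φ((3.43 − 2.57)/(SD × √(2/n)) − 1.96). At SD 3.97 this is 10% at 21 per arm and 14% at 31.5, against 2.5% without dilution. The 25% is an illustration; the documents give no figure for dilution.

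**The case for a change.** The best case for a change is that this rule carries the trial's one confirmatory claim and the design figures depend on the missing choice. If both sets must pass, power at SD 3.97 is about 54% to 56%, not 80%. If a pass in either sufficed, the one-sided error at the margin would be about 4%, not 2.5%. The documents also lean towards ITT: power is tied to people assessed, and everyone randomised is followed. Per-protocol is selected after randomisation, which is a sounder reason to distrust it than its small size. Two or three sentences would close the gap.

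Most of this stands as description. The omission is real, nothing elsewhere in the document fills it, and a sentence naming the deciding set would be tidier. It does not carry through to a required change.
- The lean towards ITT is an inference. The powered group is 42 people with a post-treatment assessment, which is not the 63, and the document does not say how many of the 63 have that assessment.
- The attendance windows differ by arm because each matches its therapy's own schedule under Interventions, and the SAP says they were fixed in advance. They do not by themselves show bias; selection after randomisation is the fair criticism.
- The argument from post-randomisation selection has to be weighed against dilution, which can make ITT lenient for non-inferiority.

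**Conclusion.** No change to the plan is needed. The part that nobody would dispute, saying which set decides and how a split is read, records a policy and alters no analysis: both sets are analysed under the existing text. A careful analyst would show both estimates and intervals together and read a wide per-protocol interval as the imprecision it is. The plan's own wording supports that, because a bound above 3.43 is inconclusive and does not contradict a pass in ITT. The reverse case, per-protocol rescuing a failed ITT, has a probability of about 1% to 2% at SD 3.97.

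The part with substance, ITT alone decides and per-protocol has no veto, is a judgement between two known weaknesses: selection in per-protocol and dilution in ITT. The plan's use of both sets is a fair way to handle that trade-off. The document is also written in the past tense with the achieved counts of 63 and 24, so a rule added now would be post hoc and could not give the protection that prespecification is meant to give.

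The figures rest on an SD of 3.97 inferred from the stated power at one-sided 0.025, equal SD in both sets, and per-protocol as a random subset. They describe sampling noise only, not selection into per-protocol, and mixed-model intervals would differ somewhat.

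### The non-inferiority interval uses an unadjusted difference in ISI change; adjusting for baseline ISI, held on every participant, could narrow it at almost no cost

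*Combined protocol and SAP*

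**What the plan says.** Hypothesis 2 is set on the change score: "BBTI will be non-inferior to CBTI based on ISI change score from pre- to post-treatment". The decision rule in the Statistical Analysis Plan follows it: "To establish BBTI as non-inferior to CBTI, the upper bound of the 95% confidence interval of the mean" difference in ISI change (CBTI minus BBTI) must not exceed 3.43. It adds: "If the upper bound of the confidence interval exceeds the NIM, non-inferiority cannot be declared (inconclusive").

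The one model described is "Linear mixed models (LMM) were used to test the main effects of treatment (CBTI vs. BBTI), time (baseline vs. post-treatment"), with the treatment-by-time interaction. Neither baseline ISI nor any other covariate is listed, and the plan does not say which model produces the decisive interval.

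Baseline ISI is available for everyone. The Measures section has the ISI "administered at baseline, in-person treatment sessions, one-week post-treatment, and the 3-month and 12-month follow-up assessments", and the Participants section makes it an entry criterion: eligible Veterans met the diagnostic criteria "and had an ISI ≥15".

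Under Randomization and Sample Size, allocation is stratified by age group and by "use of a prescription sedative-hypnotic medication (yes or no"). Baseline ISI is not a stratum. The planned size is 56 randomised, "with 42 (n=21/group) completing post-treatment assessment to achieve 80% power".

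**The concern.** A difference in change scores is the special case of a baseline-adjusted comparison in which the slope of post-treatment ISI on baseline ISI is fixed at 1. If the true slope differs from 1, a chance baseline difference between the arms passes into the estimate and adds variance. Including baseline in the mixed model as an outcome does not prevent this.

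The trial's verdict depends on one confidence bound, and it was planned on 21 completers per arm, with 12 per arm in the per-protocol set. Avoidable width in the interval therefore turns directly into a higher chance of an inconclusive result. The issue is efficiency only: the planned estimator is unbiased under randomisation, and using it does not make a false claim of non-inferiority more likely.

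**Working it through.** **Inputs from the documents.** Margin 3.43; 80% power; 21 completers per arm; 25% attrition; 1:1 allocation; two-sided 95% interval (one-sided 0.025); ITT n = 63; per-protocol n = 24 (12 per arm).

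**Not in the documents, so assumed.** The SDs of ISI and of its change, the pre/post correlation ρ, the sample-size alpha and the assumed true difference (taken as 0). Write k for post-treatment SD divided by baseline SD. Ranges used: ρ = 0.3 to 0.7 and k = 1 to 2. The entry floor of 15 restricts the baseline spread, so k is probably above 1.

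**The plan's own figures.** The attrition step reproduces: 42 / 0.75 = 56. The 21 per arm cannot be rebuilt without an SD. Solving backwards at one-sided 0.025 gives an SD of change of 3.43 × √(21/2) / (1.960 + 0.842) = 3.97 by the normal approximation, or 3.87 by the t-test. With 3.97, the unadjusted 95% half-width is 1.96 × 3.97 × √(2/21) = 2.40.

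**Does the named model adjust for baseline?** A simulated data set with 21 complete pairs per arm was analysed both ways. The treatment-by-time term and the plain difference in change agreed: estimate −1.129, SE 1.158 by both. So the interval is unadjusted whether it comes from the mixed model or from a simple change-score comparison.

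**Gain from adjustment.** The large-sample variance ratio, adjusted over change score, is

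VR = k²(1 − ρ²) / (1 + k² − 2ρk) = 1 − (1 − ρk)² / (1 + k² − 2ρk).

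It never exceeds 1, and equals 1 only when the slope ρk is 1. For example, k = 1 and ρ = 0.3 gives 0.91 / 1.40 = 0.650.

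| k | ρ = 0.3 | ρ = 0.5 | ρ = 0.7 |
|---|---|---|---|
| 1 | 0.650 | 0.750 | 0.850 |
| 1.3 | 0.805 | 0.912 | 0.991 |
| 1.5 | 0.871 | 0.964 | 0.998 |
| 2 | 0.958 | 1.000 | 0.927 |

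**Small-sample cost.** Estimating the slope multiplies the variance by about 1 + 1/(N − 4), which is 1.026 at N = 42 and 1.050 at N = 24, and uses one error degree of freedom. The ratio of interval widths (adjusted over unadjusted) at N = 42 then becomes:

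| k | ρ = 0.3 | ρ = 0.5 | ρ = 0.7 |
|---|---|---|---|
| 1 | 0.817 | 0.878 | 0.935 |
| 1.3 | 0.910 | 0.968 | 1.009 |
| 1.5 | 0.946 | 0.996 | 1.013 |
| 2 | 0.992 | 1.014 | 0.976 |

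At N = 24 the worst case is about 2.8% wider.

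**Power.** In large samples, power = Φ(2.8016/√VR − 1.96). This gives 0.935 at k = 1, ρ = 0.3; 0.851 at k = 1.5, ρ = 0.3; and 0.800 at k = 2, ρ = 0.5.

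**Simulation.** Setting: 40,000 trials per cell, bivariate normal scores, SD of change 3.87, true difference 0, baseline ISI as the only covariate.

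| | Variance ratio | Width ratio | Power, adjusted | Power, change score |
|---|---|---|---|---|
| 21 per arm | 0.664 to 1.025 | 0.816 to 1.014 | 0.930 to 0.789 | 0.80 |
| 12 per arm | 0.685 to 1.050 | – | 0.710 to 0.526 | about 0.55 |

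The first figure in each range is k = 1, ρ = 0.3; the second is k = 2, ρ = 0.5.

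**The case against.** The strongest reply is that this is a preference, not an error. The hypothesis and the rule agree with each other, and the estimator is valid. That is correct, and the point claims no more than lost precision.

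The second reply is that the largest gain needs k = 1 and ρ = 0.3, while the entry floor makes k above 1 more likely. This also stands. Over the cells with k = 1.3 to 2, the interval at 21 per arm runs from 9% narrower to 1.4% wider and is wider in 3 of 9 cells. At 12 per arm it runs from 8% narrower to 2.8% wider and is wider in 5 of 9. The case rests on a lopsided trade, not on a large expected gain.

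Third, the calculation covers baseline ISI alone. Adding the two stratification factors was not costed. If all three covariates were uninformative and varied freely, the variance factor at N = 42 would be about 1 + 3/36 = 1.083, or roughly 4% in width. Stratified allocation should keep the cost below that, but this is why those factors are only a preference here.

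Fourth, the power figures use 21 per arm, whereas 63 were randomised. At 25% attrition that leaves 63 × 0.75 ≈ 47 completers, and with an SD of change of 3.87 unadjusted power is already about 84%. The width ratios change little.

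Fifth, absence of adjustment is inferred from the plan's silence, and the exact equality shown above holds for complete pairs; with missing post-treatment scores it need not. That supports naming the model.

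Last, the plan is written in the past tense with realised counts. An adjusted analysis adopted after outcomes are known cannot rescue an inconclusive verdict. The fix is limited accordingly.

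**Conclusion.** The concern holds, as an efficiency improvement that should be made and not as a flaw in validity. As written, the interval behind the non-inferiority decision is an unadjusted difference in change, although baseline ISI is held on every eligible participant. Over the assumed range, adjusting for it at 21 per arm would bring anything from an interval 18% narrower to one 1.4% wider. In the per-protocol set the variance ratio is 0.69 to 1.05, so a loss of up to about 5% of variance is possible when the slope is near 1.

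The power range of about 79% to 93% further assumes that 21 per arm gave 80% on the change score at one-sided 0.025 with a true difference of 0, which the plan does not state. Confidence in the direction is good. Confidence in the size is moderate at best, because the documents fix neither k nor ρ.

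**What to change.** Name one model for the non-inferiority 95% interval and let it adjust for baseline ISI: either ANCOVA of post-treatment ISI on arm and baseline ISI, or a mixed model with a common baseline mean for both arms and an unstructured covariance. In the ITT model, preferably add age group and sedative-hypnotic use.

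Define the contrast as BBTI minus CBTI in adjusted post-treatment ISI, so that a positive value means BBTI is worse. This has the same direction as the stated rule when change is taken as pre minus post. Compare its upper bound with 3.43, and report the unadjusted change-score difference alongside.

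If outcomes have already been seen, state when the adjusted analysis was specified and show it beside the original rule, not in its place.

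The cost is one Stata model statement and one sentence in the plan, with no new data. With baseline ISI as the only covariate, the statistical downside when the slope is near 1 is about 2.5% of variance at 21 per arm and 5% at 12 per arm. This change does not deal with missing post-treatment scores, which need their own provision.
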